5.2 Exclusion Criteria

1. Prior enrollment in ACTT-3 or ACTT-4. *Note: this includes subjects whose participation in ACTT was terminated early.*
2. On invasive mechanical ventilation at the time of randomization (ordinal scale category 7).
3. Anticipated discharge from the hospital or transfer to another hospital which is not a study site within 72 hours of randomization.
4. Positive test for influenza virus during the current illness (*influenza testing is not required by protocol*).
5. Subjects with a low glomerular filtration rate (eGFR), specifically:
 - a. Subjects with an eGFR 15-30 mL/min are excluded unless in the opinion of the PI, the potential benefit of participation outweighs the potential risk of study participation.
 - b. All subjects with an eGFR < 15 mL/min
 - c. All subjects on hemodialysis and/or hemofiltration at screening, irrespective of eGFR, are excluded.
6. Neutropenia (absolute neutrophil count < 700 cells/ μ L, $0.7 \times 10^3/\mu$ L).

Appendix D - ACTT-4: Baricitinib/Remdesivir vs Dexamethasone/Remdesivir

7. Lymphopenia (absolute lymphocyte count <200 cells/ μ L, $0.20 \times 10^3/\mu$ L).
8. Received five or more doses of remdesivir including the loading dose, outside of the study as treatment for COVID-19.
9. Pregnancy or breast feeding (lactating women who agree to discard breast milk from Day 1 until two weeks after the last study product is given are not excluded).
10. Allergy to any study medication.
11. Received convalescent plasma or intravenous immunoglobulin [IVIg] for COVID-19, the current illness for which they are being enrolled.
12. Received any of the following in the two weeks prior to screening as treatment of COVID-19:
 - More than one dose of baricitinib for the treatment of COVID-19;
 - Other small molecule tyrosine kinase inhibitors (e.g. imatinib, gefitinib, acalabrutinib, etc.);
 - monoclonal antibodies targeting cytokines (e.g., TNF inhibitors, anti-interleukin-1 [IL-1], anti-IL-6 [tocilizumab or sarilumab], etc.);
 - monoclonal antibodies targeting T-cells or B-cells as treatment for COVID-19.

Note: receipt of anti-SARS-CoV-2 mAb prior to enrollment (e.g. bamlanivimab) for their current COVID-19 illness is not exclusionary
13. Use of probenecid that cannot be discontinued at study enrollment.
14. Received 6 mg or more of dexamethasone po or IV (or equivalent for other glucocorticoid) in one day, or more than one day, in the 7 days prior to time of randomization. *Note: 6 mg dexamethasone dose equivalents include 40 mg prednisone, 32 mg methylprednisolone and 160 mg hydrocortisone.*
15. Received ≥ 20 mg/day of prednisone po or IV (or equivalent for other glucocorticoids) for ≥ 14 consecutive days in the 4 weeks prior to screening.
16. Have diagnosis of current active or latent tuberculosis (TB), if known, treated for less than 4 weeks with appropriate therapy (by history only, no screening required).
17. Serious infection (besides COVID-19), immunosuppressive state, or immunosuppressive medications that in the opinion of the investigator could constitute a risk when taking baricitinib or dexamethasone.
18. Have received any live vaccine (that is, live attenuated) within 4 weeks before screening, or intend to receive a live vaccine (or live attenuated) during the study. *Note: Use of non-live (inactivated) vaccinations including SARS-CoV-2 vaccine is allowed for all subjects.*
19. Had a known VTE (deep vein thrombosis [DVT] or pulmonary embolism [PE]) during the current COVID-19 illness.

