 - a. Subjects with an eGFR 15-30 mL/min are excluded unless in the opinion of the PI, the potential benefit of participation outweighs the potential risk of study participation.
 - b. All subjects with an eGFR < 15 mL/min are excluded.
 - c. All subjects on hemodialysis and/or hemofiltration at the time of screening, irrespective of eGFR, are excluded.

6. Neutropenia (absolute neutrophil count <700 cells/ μ L, $0.7 \times 10^3/\mu$ L).
7. Lymphopenia (absolute lymphocyte count <200 cells/ μ L, $0.20 \times 10^3/\mu$ L).
8. Received five or more doses of remdesivir including the loading dose, outside of the study as treatment for COVID-19.
9. Pregnancy or breast feeding (lactating women who agree to discard breast milk from Day 1 until two weeks after the last study product is given are not excluded).
10. Allergy to any study medication.
11. Received convalescent plasma or intravenous immunoglobulin [IVIg] for COVID-19, the current illness for which they are being enrolled.
12. Received any of the following in the two weeks prior to screening as treatment of COVID-19:
 - More than one dose of baricitinib for the treatment of COVID-19;
 - Other small molecule tyrosine kinase inhibitors (e.g. imatinib, gefitinib, acalabrutinib, etc.);
 - monoclonal antibodies targeting cytokines (e.g., TNF inhibitors, anti-interleukin-1 [IL-1], anti-IL-6 [tocilizumab or sarilumab], etc.);
 - monoclonal antibodies targeting T-cells or B-cells as treatment for COVID-19.

Note: receipt of anti-SARS-CoV-2 mAb prior to enrollment (e.g. bamlanivimab) for their current COVID-19 illness is not exclusionary
13. Use of probenecid that cannot be discontinued at study enrollment.
14. Received 6 mg or more of dexamethasone po or IV (or equivalent for other glucocorticoids) in one day, **on more than one day** in the 7 days prior to time of randomization. *Note: 6 mg dexamethasone dose equivalents include 40 mg prednisone, 32 mg methylprednisolone and 160 mg hydrocortisone.*
15. Received ≥ 20 mg/day of prednisone po or IV (or equivalent for other glucocorticoids) for ≥ 14 consecutive days in the 4 weeks prior to screening.
16. Have diagnosis of current active or latent tuberculosis (TB), if known, treated for less than 4 weeks with appropriate therapy (by history only, no screening required).

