Appendix D - ACTT-4: Baricitinib/Remdesivir vs Dexamethasone/Remdesivir

All subjects will receive standard antiviral treatment with remdesivir as a 200 mg intravenous (IV) loading dose on Day 1, followed by a 100 mg once-daily IV maintenance dose during hospitalization up to a maximum of 10 total doses (i.e., loading + maintenance doses received during study and pre-study if applicable). See [Section 6.1.4](#) for details of dosing and dose modification.

For the baricitinib component, subjects will receive either:

- Baricitinib 4 mg** orally (po) (two 2 mg tablets) or dissolved* per NG tube, daily for the duration of the hospitalization up to a 14-day total course.
- Placebo given as two tablets** orally (po) or dissolved per NG tube, daily for the duration of the hospitalization up to a 14-day total course.

** See MOP for instructions on how to prepare and administer baricitinib to patients having difficulty swallowing*

*** Dose of oral study product will be decreased or held based on eGFR. Specifically:*

| eGFR Value | Dose of Baricitinib/Oral Placebo |
|--|---|
| ≥60 mL/min | Two tablets (4 mg total) once daily No dose adjustment |
| 30 - <60 mL/min | One tablet (2 mg) once daily |
| 15 - <30 mL/min | One tablet (2 mg) QOD – every other day |
| <15 mL/min or require hemodialysis or hemofiltration | Hold oral study product |

For the dexamethasone component, subjects will receive either active product or placebo as follows:

- Dexamethasone will be administered as a 6 mg slow IV push over 3 to 5 minutes (1.5 mL) daily for the duration of the hospitalization up to a 10-day total course.
- A normal saline placebo will be given as a slow IV push over 3 to 5 minutes daily for the duration of the hospitalization up to a 10-day total course
- If local standards use other means of administration (such as IV infusion), these may be used for both active and placebo.
- Any pre-study dexamethasone (max 1 dose per inclusion criteria) is not counted towards the 10 day course.

Duration of therapy:

- IV remdesivir – 5 - 10 days while hospitalized.
 - The recommended treatment duration for most subjects is 5 days.
 - If a patient does not demonstrate clinical improvement, or deteriorates to require invasive mechanical ventilation and/or extracorporeal membrane oxygenation (ECMO), treatment may be extended for up to 5 additional days for a total treatment duration of up to 10 days.
- Oral baricitinib (or oral placebo) – 14 days while hospitalized.

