- If a patient has received dexamethasone the day prior to enrollment, then the baricitinib/po placebo and dexamethasone/IV placebo can be administered right after randomization and this becomes Day 1.
- If a patient has received dexamethasone at any time on the day of enrollment but before randomization/enrollment, then there are several options as described below.
 - It is preferred to randomize and give remdesivir + dexamethasone/po placebo + baricitinib/IV placebo on the same calendar day as randomization. This could result in subjects receiving two doses of dexamethasone on Day 1 (a pre-study dose and an on-study dose of dexamethasone/IV placebo).

- If the site is concerned with this high dose of dexamethasone, sites have 24 hours between randomization (enrollment) and initial study product administration (i.e. both drugs may be delayed until the calendar day after randomization but within 24 hours of randomization).
- Alternatively, if necessary (but not preferred), sites may randomize and give remdesivir and baricitinib/po placebo on the same calendar day as randomization (this becomes Day 1) and on Day 2, give all other study products and submit a protocol deviation for missed dose of IV push study product on Day 1 and this missed dose of dexamethasone/IV placebo will not be made-up during the study. The subject will receive only 9 doses of dexamethasone/IV placebo from Day 2 through Day 10. This option allows the PI to decide the risk /benefit ratio of a potential double dose of dexamethasone on Day 1 for their patients.

For the baricitinib component, subjects will receive either active product or placebo as follows:

- Baricitinib will be administered as a 4 mg orally (po) (two, 2mg tablets) or dissolved for NG tube, daily for the duration of the hospitalization up to a 14-day total course.
- A placebo will be given as two tablets po or dissolved for NG tube, daily for the duration of the hospitalization up to a 14-day total course.
- See [Section 6.1.4](#) for dosing modifications for baricitinib for renal failure.
- See MOP for instructions on how to prepare and administer baricitinib to patients having difficulty swallowing

For dexamethasone component, subjects will receive either active product or placebo as follows:

- Dexamethasone will be administered as a 6 mg slow IV push over 3 to 5 minutes daily for the duration of the hospitalization up to a 10-day total course.

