- A placebo will be given as an equal volume normal saline, as a slow IV push daily for the duration of the hospitalization up to a 10-day total course.
- If local standards use other means of administration (such as IV infusion), these may be used for both active and placebo after approval of the sponsor. Reports of intense perineal pain and/or burning are reported immediately after given IV push too quickly.
- Any pre-study dexamethasone (see exclusion criteria) is not counted towards the 10 day course.

Duration of therapy:

- IV remdesivir – up to 10 days while hospitalized (i.e., maximum of 10 total infusions pre-enrollment and during study).
- Oral baricitinib (or oral placebo) – 14 days while hospitalized (i.e., maximum of 14 total doses).
- IV dexamethasone (or IV placebo) – 10 days while hospitalized (i.e., maximum of 10 total doses).
- All medications stop on discharge from hospital.
 - Of note, if a subject is retained in the hospital for non-COVID-19 related issues and no longer requires supplemental oxygen and ongoing medical care (i.e., ordinal scale category 3), the PI may decide to discontinue all medications.

- If readmitted after discharge, see [Section 7.4](#).

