The overall eligibility of the subject to participate in the study will be assessed once all screening values are available. The screening process can be suspended prior to complete assessment at any time if exclusions are identified by the study team.

Study subjects who qualify will be randomized in the Advantage eClinical system, and all others will be registered as screen failures. The ordinal scale should be done at the time of randomization; the site will need this data to randomize the subject in eClinical. The study team has 24 hours to complete other Day 1 baseline assessments prior to the first study product administration including the collection of the OP swab and blood and completing or recording a baseline physical examination that was done, including weight and height (height can be self reported). Clinical laboratory tests collected as part of routine care of the patients in the 36 hours prior to first dose qualify for baseline safety tests on Day 1.

If a subject is found to be ineligible AFTER being randomized and they did not receive any study product, the site should file an early study termination and stop all study procedures including specimen collection.

If the subject is found to be ineligible AFTER being randomized and did receive study product, they may continue on study if the PI has no safety concerns with their continued participation. The site should file a study protocol deviation (i.e., checkbox: met exclusion criteria). However, if the PI feels that the risk of participation outweighs the benefit, the site should file an early study termination.

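### ACTT-4 exclusion 14 in Appendix D Section 5.2 shuts out patients with exactly one day of dexamethasone at 6 mg or more, whom the synopsis admits and the dosing rules expect

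*Protocol*

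**What the plan says.** All references are to Appendix D (ACTT-4) of the protocol.

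- **Section 5.2, item 14** excludes patients who received 6 mg or more of dexamethasone, oral or IV, or an equivalent glucocorticoid dose, "in one day, or more than one day, in the 7 days prior to time of randomization".
- **Section 1.1 (synopsis), item 14** has the same dose and the same 7-day window, but the condition is "in one day, on more than one day in the 7 days prior to time of randomization". The phrase about more than one day is set in bold.
- **Section 1.1, Study Intervention:** "Any pre-study dexamethasone (max 1 dose per inclusion criteria) is not counted towards the 10 day course".
- **Section 6.1.2** gives instructions for patients already treated with dexamethasone in routine care. For treatment the day before: "If a patient has received dexamethasone the day prior to enrollment, then the baricitinib/po placebo and dexamethasone/IV placebo can be administered right after randomization". For treatment on the day of enrollment, the preferred option is to randomize and dose on the same calendar day, with the remark: "This could result in subjects receiving two doses of dexamethasone on Day 1 (a pre-study dose and an on-study dose of dexamethasone/IV placebo". It then adds: "Any pre-study dexamethasone (see exclusion criteria) is not counted towards the 10 day course".
- **Section 8.1.1** says what to do if a subject is found ineligible after randomization. If no study product was given, "the site should file an early study termination and stop all study procedures including specimen collection". If product was given, the subject may continue when the investigator has no safety concern, and a deviation is filed. Early termination follows if the investigator judges that risk outweighs benefit.
- **Section 9.4.7** plans a subgroup analysis by dexamethasone use before randomization.

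**The concern.** Section 5.2 is the formal eligibility list. Its wording and the synopsis wording reverse each other for one type of patient, and nothing in the protocol says which list governs. Two sites could reach opposite decisions on the same patient, each with the protocol's support.

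A site that applies Section 5.2 literally turns away a patient the trial meant to enroll. That slows recruitment, changes the mix of prior exposure and shrinks the prior-dexamethasone subgroup.

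If the single day comes to light after randomization, the Section 8.1.1 rules apply to a patient who should never have been called ineligible. In the branch without study product, all procedures stop. Because the primary population in Section 9.3 is everyone randomized, each such termination loses follow-up in the primary analysis. Exclusion 1 then bars that person from re-enrolling, since it covers subjects whose participation was terminated early.

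**Working it through.** No sample size, power or alpha figure bears on this point, so there is nothing to recompute. The check applies each version of item 14 to every possible patient and then asks which version the rest of the appendix fits.

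**Step 1. Apply both versions.** Count the days in the 7 before randomization on which the patient received 6 mg or more of dexamethasone or equivalent.

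| Qualifying days | Synopsis item 14 | Section 5.2 item 14 | Agree? |
|---|---|---|---|
| 0 | not excluded | not excluded | yes |
| 1 | not excluded | excluded | **no** |
| 2 or more | excluded | excluded | yes |

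The versions conflict in one of the three cases: exactly one day.

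**Step 2. Test whether Section 5.2 can be read the synopsis way.** It cannot. If one day is enough to exclude, the added clause about more than one day does no work. That redundancy suggests a slip of *or* for *on*, but the sentence as printed still excludes at one day. Both lists are current text, so this is not a difference from a superseded version.

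**Step 3. Ask which version the other text supports.**

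- The synopsis dosing text allows one pre-study dose.
- Section 6.1.2 gives dosing rules for patients treated the day before or on the day of enrollment.
- It describes the resulting Day 1 exposure as a high dose and a potential double dose. The on-study dose is 6 mg daily. A doubling of that dose implies a pre-study dose of about 6 mg, since 6 mg + 6 mg = 12 mg is twice the study dose.
- Section 2.1.1 describes the dexamethasone regimen in the cited UK open-label trial as 6 mg once daily, so a routine-care dose of 6 mg is the natural reading.
- A patient with one 6 mg dose the day before or on the day of enrollment has exactly one qualifying day. Section 6.1.2 tells sites how to dose that patient; Section 5.2 excludes the same patient.

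**Step 4. Size.** The number of patients cannot be calculated. The protocol gives neither the number screened nor the share with exactly one qualifying day. The 1382 subjects and the planned total of about 1500 in Section 9.2 do not depend on item 14.

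**The case against.** The strongest reply is that the slip corrects itself. The Section 5.2 sentence is visibly redundant, the synopsis prints the operative phrase in bold, and a site that reads Section 6.1.2 must see that prior dexamethasone is not a blanket bar. The eligibility form and the Manual of Procedures, which are not visible here, may carry the right rule. This stands in part: the protocol shows that a literal reader of Section 5.2 would err, not how many sites would. It does not remove the contradiction.

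Second, Section 6.1.2 never states the pre-study dose in milligrams, and a dose below 6 mg passes both versions. This is correct, so the reading that a full dose is meant is an inference. It is well supported by the references to a high or double dose against a 6 mg study dose.

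Third, the one-dose allowance in the synopsis does not match synopsis item 14 exactly, because one counts doses and the other counts days at or above a threshold. Two 6 mg doses on one day, or 4 mg on each of three days, pass synopsis item 14 but exceed one dose. This stands and bears on the fix.

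Fourth, the consequence after randomization is milder than termination when product has been given, since the subject may continue with a deviation filed. This also stands.

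**Conclusion.** The point holds. Item 14 in Appendix D Section 5.2 is wrong as written and contradicts the synopsis for patients with exactly one qualifying day. That the synopsis is the intended rule rests on the one-dose allowance and on reading the pre-study dose in Section 6.1.2 as roughly the 6 mg study dose.

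The consequences are operational: recruitment, the mix of prior exposure, the size of one planned subgroup, and avoidable terminations or deviations. The number of patients is unknown. The randomized comparison stays valid, because eligibility is to be judged before assignment and the primary analysis includes everyone randomized. Sample size and power are unchanged. It should be fixed because it is a wrong threshold in the formal eligibility list and costs almost nothing to correct.

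**What to change.** 1. In Appendix D Section 5.2 item 14, replace the condition with the synopsis wording: "in one day, on more than one day in the 7 days prior to time of randomization".
2. In the synopsis sentence on pre-study dexamethasone, refer to the exclusion criteria rather than the inclusion criteria, as Section 6.1.2 already does. Either drop the one-dose limit there or restate it in the terms of item 14, so that a count of doses is not attributed to a criterion that counts days.
3. State that a patient with exactly one qualifying day is not excluded by item 14, and that enrolling such a patient is not a protocol deviation. Items 15 and 17 may still exclude that patient on other grounds.

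Sections 6.1.2 and 9.4.7 need no change. The cost is one clarification letter or minor amendment, with no new data and no change to the analysis.

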5.2.1 Exclusion of Specific Populations

Information about the epidemiology of COVID-19 indicates that the largest burden of severe disease requiring hospitalization occurs among older adults, especially those with comorbidities. The incidence of severe morbidity and mortality among children and adolescents is low, and the clinical spectrum and natural history of COVID-19 among children and adolescents is not well understood. There is also limited data about the use of anti-inflammatory medications such as dexamethasone or baricitinib in children. Due to these gaps in knowledge of the disease in this population, a low incidence of severe disease, and an inability to justify a benefit to this population, children and adolescents will not be included in this trial.

In nonclinical reproductive toxicity studies, remdesivir demonstrated no adverse effect on embryo-fetal development when administered to pregnant animals. Embryonic toxicity was seen when remdesivir was initiated in female animals prior to mating and conception, but only at a systemically toxic dose. Remdesivir has not been studied in pregnant women. While baricitinib is a licensed drug with a known safety profile, the limited human data on use of baricitinib in pregnant women are not sufficient to inform a drug-associated risk for major birth defects or miscarriage. A short course of dexamethasone is routinely used to decrease neonatal complications of prematurity in pregnant women with threatened preterm delivery and is generally well tolerated in pregnant women.(43) Infants born of mothers who have received substantial doses of corticosteroids during pregnancy should be carefully observed for signs of hypoadrenalinism. Because the effects of remdesivir and baricitinib on the fetus and the pregnant woman are not fully known, pregnant women will not be eligible for the trial.

In animal studies, remdesivir metabolites have been detected in the nursing pups of mothers given remdesivir. Baricitinib is present in the milk of lactating rats. There is no information available on the presence of baricitinib in human milk or the effects of the drug on the breastfed infant. Dexamethasone has been used in lactating women. Corticosteroids appear in breast milk and could suppress growth, interfere with endogenous corticosteroid production, or cause other unwanted effects. Because the effects of remdesivir and baricitinib on the breastfeeding infant is not known, women who are breast feeding will not be eligible for the trial unless they agree to discharge breast milk from Day 1 until 2 weeks after the last dose is administered.

